1. **Survey Questionnaires**: The interviews will include questions about medical history, tobacco use, and questionnaires about mood. Answering these personal questions could make the participant feel uncomfortable.
2. **Breach of Confidentiality**: The risk of the interview is loss of privacy if other people find out the results.
3. **Smoking Cigarettes**: All cigarettes are detrimental to a person's health and can lead to severe or fatal medical problems including:
 - a. **Cardiovascular diseases**: Coronary heart disease, heart attack, stroke, peripheral vascular disease, reduced blood circulation, abdominal aortic aneurysm
 - b. **Respiratory diseases**: Emphysema, bronchitis, tuberculosis and chronic airway obstruction
 - c. **Cancers**: Lung, bladder, liver, colon, cervical, esophageal, kidney, larynx, mouth, pancreatic, throat, stomach cancers and acute myeloid leukemia
 - d. **Diabetes**
 - e. **Abnormal immune function, rheumatoid arthritis**
 - f. **Other health risks including but not limited to infertility, ectopic pregnancy, lower bone density in postmenopausal women, hip fracture in women, male sexual dysfunction, age-related macular degeneration, blindness and cataracts.**
4. **Use of Vaping Devices**: can expose users to several chemicals including nicotine, carbonyl compounds, and volatile organic compounds, known to have adverse health effects. The health effects and potentially harmful doses of heated and aerosolized constituents of e-liquids, including solvents, flavorants, and toxicants, are not completely understood. Vaping device aerosol is not harmless "water vapor" although it generally contains fewer toxicants than combustible tobacco products. Specific potential known risks include
 - a. Vaping devices contain nicotine which may contribute to some of the disease associated with smoking
 - b. The most common side effects related to vaping devices are changes in taste, mucus in throat/sinus, dry mouth, dry cough, throat irritation, sore throat, mouth ulcers, dizziness, headache, and nausea.
 - c. On rare occasions, batteries from vaping devices have exploded/ignited and injured users

- d. Vaping devices can overheat and present minor burn risks if the button is turned on repeatedly. Participants are told to be careful if storing the device in a place where the button might accidentally be pressed often.
- e. Ingestion of e-liquids containing nicotine can cause acute toxicity and possible death if the content of the cartridges containing nicotine are consumed.
- f. Participants are told to keep study vaping devices and all e-liquids away from children and pets.

5. **Use of Medicinal Nicotine:** Most common adverse effects for medicinal nicotine include irregular heartbeat/palpitations, high blood pressure, mouth sores, mouth or throat irritation, heartburn, upset stomach, vomiting, diarrhea, dizzy or lightheadedness, and hiccups or belching. Additional adverse effects associated with nicotine gum include teeth or jaw problems. There may also be a risk of nicotine toxicity including symptoms such as nausea, dizziness, vomiting, diarrhea, and weakness.

6. **Dual use of tobacco or nicotine products:** There is also the chance of use of more than one product and/or continued use of the products; however, cessation of all tobacco products will be strongly recommended to the participants at the end of the study.

7. **Smoking Withdrawal:** Participants may experience smoking withdrawal symptoms during this study if they decide not to purchase tobacco products. The symptoms can be uncomfortable but are typically of minimal risk. Smoking withdrawal symptoms include:

- a. Anger, irritability, frustration
- b. Anxiousness, nervousness
- c. Depressed mood or sadness
- d. Desire or craving to smoke
- e. Difficulty concentrating
- f. Increased appetite, hunger or weight gain
- g. Insomnia, problems sleeping or waking at night
- h. Restlessness
- i. Impatience
- j. Constipation
- k. Dizziness
- l. Coughing
- m. Dreaming or nightmares
- n. Nausea
- o. Sore throat

8. **Returning to Regular Smoking:** It is possible that if participants return to smoking their usual brand of cigarette at the end of the study they may experience mild and transient nausea, dizziness, and lightheadedness.

9. **Changes in Mood, Emotions and Psychiatric Symptoms:** Smoking and nicotine can affect a person's mood and emotions and are associated with psychiatric disorders including major depressive disorder, general anxiety disorder, bipolar disorder and eating disorders. Any changes in nicotine use or cigarette consumption could adversely affect mood, emotions and the symptoms related to psychiatric conditions in some individuals.

10. **Smoking and Oral Contraceptives in Women:** Women who smoke and are over the age of 35 should not take oral contraceptives that contain estrogen without consulting their

physician. Smoking while using oral contraceptives can increase the risk of having a cardiovascular event such as a heart attack or stroke. Additionally, there is a potential risk of thrombosis associated with hormonal therapy (including contraceptives) and smoking.

Avoiding Risks during Pregnancy

Smoking during pregnancy can lead to miscarriage, preterm delivery, stillbirth, birth defects, and other problems. To avoid risks to the participant and fetus, female participants will be tested for pregnancy at the Screening Visit.

Expected benefits of participation

There are no immediate benefits from participating in the study. The information obtained from this study may ultimately help the Food and Drug Administration (FDA) decide how best to regulate tobacco products with the goal of improving public health.

Reporting Unanticipated Problems, Adverse Events or Deviations

Identifying Adverse Events

While participating in the study, adverse events will be assessed at Virtual Visit 6 and carbon monoxide levels from In-Person Lab Visit 3. Adverse events will typically be identified during the administration of the Health Changes Questionnaire. Other adverse events may be identified by spontaneous reports from the participant. Withdrawal symptoms are considered an adverse event if the symptom had a significant impact on the participant's daily life, caused a major disruption of functioning, or took any medication for it.

- Health Changes Questionnaire: If the participant answers "YES" to Questions 1, 2, or 3 the interviewer should assess for adverse events.
 1. Have you had any negative changes in your physical or mental health since your last virtual visit? If yes, briefly describe.
 2. Since your last virtual visit, have you received any form of medical care? If yes, briefly describe.
 3. Have you had any changes in medication since your last visit?

Physiological data that will be reviewed:

1. CO level: The 'Adverse Event Form' will be completed if the average of two (or three) consecutive measurements in the same visit is:
 - o CO is greater than 50 ppm if CO at Screening/Baseline Visit is < 20 ppm.
 - o CO is greater than 60 ppm if CO at Screening/Baseline Visit is 20 – 34 ppm.
 - o CO is greater than 70 ppm if CO at Screening/Baseline Visit is 35 – 49 ppm.

For the participant's protection, participants will be withdrawn immediately from the study if any of the following occur:

1. Cardiovascular disease (CVD) event: Typically includes MI (heart attack), PTCA (angioplasty/stenting), bypass surgery, stroke, peripheral vascular disease (arterial

blockages in arms or legs leading to procedure or surgery). Less common CVD problems would be new cardiac arrhythmias (e.g., new atrial fibrillation) or new valvular disease (e.g., mitral or aortic regurgitation).

2. DVT/PE (deep vein thrombosis/pulmonary embolism, i.e., blood clots in the venous system).
3. Suicide Attempt: A participant will be withdrawn if they attempt suicide at any time during participation in the study
4. Psychiatric Hospitalization: A participant will be withdrawn if they are hospitalized for psychiatric reasons at any time during participation in the study.
5. Pregnancy: If a participant indicates they are pregnant at Virtual Visit 6 or In-Person Lab Visit 3, they will be withdrawn from the study, and this event will remain open until delivery. At that time the license medical monitor will contact the participant to ask a few questions about the baby's health and will update the open 'Adverse Event Form'.

The following will be monitored and can lead to the participant being withdrawn by the PI or Licensed Medical Monitor:

1. Expired breath CO >80 ppm
2. Any hospitalization or debilitation in which participation in the study could be detrimental to the recovery process. This will be self-reported by the participant and will be reviewed by the site PI and medical monitor to determine whether continued participation in the study is appropriate.
3. If a participant is behaving in an inappropriate or threatening manner, admits to lying about eligibility criteria, including omitting previous medical diagnoses and medications, is participating in other smoking research studies that could affect the primary outcome measures, does not follow study instructions, etc., then the PI can withdraw them from the study at the PI's discretion.
4. If a participant fails to attend her/his Virtual Visit 1 within the 21-day allowable visit window, they will not be eligible to reschedule the visit or continue participation in the study.

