Aim 1: To determine how the availability of menthol e-liquids affects combusted tobacco purchasing in menthol cigarette smokers. *Hypothesis 1: Non-menthol cigarette purchasing will be greatest when only tobacco e-liquids are available, indicating that the availability of menthol e-liquids is important for encouraging menthol cigarette smokers to switch to potentially less harmful products.*

Aim 2: To establish if the availability of mint e-liquids is beneficial to menthol cigarette smokers. *Hypothesis 2: Non-menthol cigarette purchasing will not differ by more than 10% when only menthol e-liquids are available compared to when menthol and mint e-liquids are available, indicating that banning mint e-liquids would not discourage menthol cigarette smokers from switching to potentially less harmful products.*

Exploratory Aim: To evaluate the effect of menthol and mint e-liquid restrictions among black menthol cigarette smokers. The effects of the e-liquid marketplace manipulation will be replicated among black smokers.

METHODS AND MEASURES

Overall Study Design

We propose to conduct a within-subjects, multi-session virtual lab study and validation field assessment to determine how the availability of menthol and mint e-liquids affects product purchasing among menthol cigarette smokers. Adult daily menthol cigarette smokers (N=80) will be recruited for this study. After initial eligibility is assessed, participants will complete six virtual sessions (1 baseline, 4 experimental, and 1 follow-up), with three in-person components, and one field assessment to evaluate their tobacco use.

Design and Setting

Participants will be recruited from Winston-Salem, NC and the surrounding area using advertisements on public transit, community flyers, and social media. In a recent trial conducted in Winston-Salem enrolling daily cigarette smokers using similar recruitment methods (U54DA031659; PI: [name]), over 60% of participants were menthol cigarette smokers and 31% identified as black or African American. In-person lab visits to drop off biosamples and pickup study products will be conducted at the Wake Forest Tobacco Control Center of Excellence located in Biotech Place in the Innovation Quarter.

Subject Selection Criteria

We anticipate recruiting up to 100 participants to achieve 80 completers. Equal numbers of black and white participants will be enrolled.

Inclusion criteria:

1. 21+ years of age

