2. Self-report smoking at least 5 cigarettes per day for the past year
3. Self-report smoking menthol cigarette brands > 80% of the time
4. Breathe carbon monoxide (CO) level > 8 ppm or positive urine NicCheck
5. Willingness to use other tobacco products during the study
6. Speak, comprehend, and read English sufficiently to complete study procedures
7. Have home access to a computer, smart phone, or tablet with a web camera and internet access

Exclusion criteria:

1. Currently seeking treatment to quit smoking
2. Self-reported serious medical or psychiatric condition(s) including cardiovascular and chronic respiratory diseases
3. Body temperature > 100.4 F

4. Cold, flu or COVID-19 symptoms including fever, cough, and runny nose in the past 30 days
5. Currently pregnant, breastfeeding or intending to become pregnant for the duration of the study or unwilling to agree to use adequate protection to avoid pregnancy
6. CO reading > 80 ppm
7. Enrollment stratum (Non-Hispanic, white or Black/African American)

Individuals who report smoking non-menthol flavored cigarettes will be excluded since the purpose of the trial is to understand how menthol and mint e-liquid flavor restrictions affect menthol cigarette smokers. We plan to enroll equal numbers of white and African-American/Black participants so we will exclude individuals once the stratum is full (i.e. 40 enrolled). Those with unstable medical or psychiatric conditions are excluded as these symptoms could affect a participant's ability to complete the study. We will exclude those indicating immediate readiness to stop smoking, as participation in this study may not lead to reductions in smoking. We will exclude pregnant people, those trying to become pregnant and those currently breastfeeding due to the potential harmful effects of tobacco use on developing fetuses and infants. Because participants are required to complete portions of the protocol independently during the virtual lab sessions, they will need to be able to independently read and comprehend the study materials.

Those who report past 30 day cold, flu or COVID-19 symptoms will be temporarily excluded as a safety precaution. They will be able to re-screen once they have been symptom-free for more than 30 days.

Telephone Screening Survey

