
1. Participants will complete Virtual Visit 2 between 1 and 21 days after completing In-Person Lab Visit 1. Virtual Visits 2-5 will ideally be conducted four days in a row to reduce online task fatigue. However, visits may be scheduled up to 7 days apart.

The following assessments will be administered as an interview and entered into REDCap by the interviewer:

1. Timeline Follow Back (TLFB) Questionnaire, which will assess tobacco and nicotine product use since their last virtual visit.

The following surveys will be self-administered using REDCap:

1. Minnesota Nicotine Withdrawal Scale
2. Questionnaire of Smoking Urges-Brief – Usual Brand Cigarette

Participants will complete the ETM task on the computer. If the participant needs assistance with navigating the online marketplace the research staff may screen share and allow the participant to verbally select the items that they would like to purchase. The products available on the ETM include:

- Menthol and non-menthol cigarettes (matched to the participant's preferred brand)
- Fruit, dessert, mint, menthol and tobacco e-liquids (e.g., Suorin iShare)
- Mint, fruit, and cinnamon nicotine gum (e.g., Nicorette).

Participants will undergo one of four marketplace conditions during Virtual Visits 2-5, with the order of administration randomized across participants.

- Marketplace Condition 1 includes only tobacco e-liquids.
- Marketplace Condition 2 includes menthol and tobacco e-liquids.
- Marketplace Condition 3 includes mint menthol, and tobacco e-liquids.
- Marketplace Condition 4 includes fruit, dessert, mint, menthol, and tobacco e-liquids.

Staff will instruct participants to complete the ETM task as if they are purchasing the products from a retailer, and that one iteration of the task will be randomly selected and will determine which products they will use during the field assessment. In reality, we will randomly assign which condition is used 1, 2, 3, or 4 but will assign products based on when menthol cigarettes were not available each to simulate a menthol cigarette ban.

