All participants will be emailed a cessation manual and local smoking cessation resources.

Product adherence

To verify self-reported tobacco use, all used and unused products will be collected and counted at In-Person Lab Visit 3. Discrepancies between consumption stated on the TLFB versus consumption based on the products returned will be addressed. Non-adherence (i.e., using products not purchased from the ETM) will be assessed via the TLFB and qualitative interview with the importance of honest self-reporting emphasized. If participants report not using combusted tobacco, then CO readings < 6 ppm will verify their self-report.

Compensation

Participants will be paid \$155 for completing the study. They will earn \$30 for completing Virtual Visit 1, \$15 per visit for completing Virtual Visits 2-6 plus a \$50 bonus for completing the study.

Participants that do not meet enrollment criteria at Virtual 1 will earn \$20 for attending the visit. Participants that start but do not complete the study will receive payments for the virtual visits attended. They will not receive the \$50 completion bonus.

ANALYSIS PLAN

Primary Outcome

Protocol Version 10
5.13.22

- Total amount of non-menthol cigarettes purchased when menthol cigarettes are not available.

Secondary Outcomes

- Total amount of tobacco e-liquid purchased when menthol cigarettes are not available.
- Total amount of menthol e-liquid purchased when menthol cigarettes are not available.
- Total amount of mint e-liquid purchased when menthol cigarettes are not available.
- Total amount of dessert and fruit e-liquid purchased with menthol cigarettes are not available

Exploratory Outcomes

- Mean Perceived Health Risk Scale scores
- Mean Product Evaluation Scale scores
- Mean Minnesota Nicotine Withdrawal Scale scores
- Mean Questionnaire on Smoking Urges scores
- Mean Tobacco Product Interest scores
- Mean Tobacco Policy Questionnaire scores
- Total amount of non-menthol cigarettes purchased when menthol cigarettes are not available by race
- Total amount of tobacco e-liquid purchased when menthol cigarettes are not available by race.
- Total amount of menthol e-liquid purchased when menthol cigarettes are not available by race.
- Total amount of mint e-liquid purchased when menthol cigarettes are not available by race.
- Total amount of dessert/fruit e-liquid purchased when menthol cigarettes are not available by race.
- Themes emerging from the qualitative interviews

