Sample Size/Estimation/Analysis

Power calculation

Based on prior ETM studies in which the effects of increasing cigarette price were observed in 22-40 participants, a sample size of 80 will be sufficient for answering Aims 1 and 2 as well as the exploratory racial subgroup analyses. No ETM studies have examined the impact of e-liquid flavor availability on combusted tobacco purchasing, so we do not have a direct effect size estimate for our manipulation. In our pilot study, the marketplace manipulation (menthol little cigars available vs. not) resulted in a small effect size (Cohen's $d = 0.31$), likely because JUUL pods were overwhelmingly preferred. When comparing mean menthol/mint e-liquid purchasing vs mean tobacco e-liquid purchasing, there was a large effect size ($d = 1.2$). Thus, we anticipate that our proposed marketplace manipulation will be associated with at least a medium effect size ($d = 0.5$) for non-menthol cigarette purchasing and a sample size of 80 will be sufficient for detecting differences.

For Aim 1 comparing within-participant impact of menthol e-liquid availability on mg of nicotine purchased, our proposed sample size of 80 will have 80% power to detect differences as small as $d=0.31$ using a paired t-test assuming type I error set to 0.05.

Aim 2 hypothesizes that nicotine purchased will be nearly equivalent when mint e-liquid is available or not. Framing the question as an equivalence test, we set a region of equivalence to be [-0.33, 0.33] standard deviations for the difference in effect with the addition of mint. Employing a paired t-test with type I error set to 0.05, our planned sample size of 80 will have 80% power to reject the null that there is an effect outside of [-0.33, 0.33] in favor of the alternative that the effect lies in [-0.33, 0.33]. In the context of mg of nicotine, this would map to an equivalence region of [-20, 20] mg of nicotine, assuming a standard deviation of 60 mg. In other words, we are sufficiently powered to conclude equivalence between mg of nicotine purchased with and without mint available.

Statistical analysis plan

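### Closing each race stratum at 40 enrolled conflicts with recruiting up to 100 for 80 completers, and leaves the 80 assumed in the power calculation reachable only with zero loss after enrolment

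*Combined protocol and SAP*

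**What the plan says.** All references are to the combined protocol and SAP.

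- **Overall Study Design:** "Adult daily menthol cigarette smokers (N=80) will be recruited for this study".
- **Subject Selection Criteria, opening lines:** "We anticipate recruiting up to 100 participants to achieve 80 completers", with equal numbers of black and white participants.
- **Subject Selection Criteria, text after the exclusion list:** "we will exclude individuals once the stratum is full (i.e. 40 enrolled"). Stratum is also item 7 of the exclusion criteria, so the cap operates as an eligibility rule.
- **Power calculation, Aim 1:** "our proposed sample size of 80 will have 80% power to detect differences" down to d=0.31, by paired t-test with type I error 0.05.
- **Power calculation, Aim 2:** "our planned sample size of 80 will have 80% power to reject the null" of a difference outside ±0.33 SD.
- **Compensation:** "Participants that start but do not complete the study will receive payments for the virtual visits attended".
- **Virtual Visits 2-5:** the four marketplace visits are ideally on consecutive days. "However, visits may be scheduled up to 7 days apart". The first may fall up to 21 days after In-Person Lab Visit 1.

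The terms recruited, enrolled and completer are not defined, and there is no rule for replacing people who drop out.

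**The concern.** Three numbers have to fit together: how many people may enter, how many are expected to finish, and how many the power calculation assumes. The cap sets the first at 80 and the power calculation sets the third at 80, so the expected loss between them must be zero. Yet the plan provides for loss. It sets payment for people who start and do not finish, lists grounds for withdrawal, and aims to recruit more people than it expects to complete.

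In practice, staff applying the stratum rule literally would turn away the people needed to reach 80 completers. At stake is mainly the Aim 2 equivalence conclusion, whose power is only just 80% at n=80.

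**Working it through.** **Inputs.** Cap of 40 per stratum, two strata, 100 recruited and 80 completers (Subject Selection Criteria). Aim 1: d=0.31, paired t-test, alpha 0.05, n=80. Aim 2: margin 0.33 SD, alpha 0.05, n=80 (Power calculation). The anticipated effect on non-menthol cigarette purchasing is at least d=0.5 (same section). Sidedness is not stated. I take Aim 1 as two-sided, and Aim 2 as two one-sided tests at 0.05 each with a true difference of zero.

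**Step 1: the counts.** 2 × 40 = 80 enrolled at most. For 80 completers, the tolerable loss is 1 − 80/80 = 0%. The 100-to-80 sentence corresponds to 1 − 80/100 = 20%, but the plan does not say at which stage those 20 people are lost.

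**Step 2: the two readings of the 100.**
- If it counts enrolled participants, it exceeds the cap by 100 − 80 = 20.
- If it counts people consented or screened, the extra 20 are used up before enrolment and none remain to cover later loss.

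**Step 3: reproduce the plan's power at n=80.**
- Aim 1: power = P(T > t₀.₉₇₅,ₙ₋₁), where T is noncentral t with n − 1 df and noncentrality d√n. At d=0.31 and n=80 this is 78.2%, close to the stated 80%.
- Aim 2: equivalence is declared when |mean difference| < 0.33 − t₀.₉₅,ₙ₋₁ × s/√n, in SD units. Integrating over the distribution of s at n=80 gives 80.0%, which matches the plan.

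**Step 4: repeat with loss from 80 enrolled.** The loss rates are assumed. The figures are complete-case.

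| Loss | n with data | Aim 1, d=0.31 | Aim 1, d=0.5 | Aim 2, true difference 0 | Aim 2, true difference 0.1 SD |
|---|---|---|---|---|---|
| 0% | 80 | 78.2% | 99.3% | 80.0% | 63.8% |
| 5% | 80 × 0.95 = 76 | 76.0% | 99.0% | 77.2% | 61.5% |
| 10% | 80 × 0.90 = 72 | 73.7% | 98.7% | 74.1% | 58.9% |
| 20% | 80 × 0.80 = 64 | 68.5% | 97.6% | 66.6% | 53.0% |

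**Step 5: which losses count.** The mixed model in the Statistical analysis plan compares Conditions 1-3 only. Loss after Virtual Visit 5, or of Condition 4 alone, therefore costs Aims 1 and 2 nothing. If someone misses only the last marketplace visit and all 24 orders are equally likely, both conditions of a given pair remain observed when the missed condition is one of the other two: 2/4 = 50%. The mixed model can use some of the remaining partial data. The longest permitted span from Lab Visit 1 to Virtual Visit 5 is 21 + 3 × 7 = 42 days, a scheduling maximum rather than the expected course.

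**Step 6: what a ceiling of 50 per stratum would give.** With 50 enrolled and independent losses, the chance of at least 40 with data in one stratum is binomial; squaring it gives the chance for both strata. At 5% loss it is over 99% for both. At 10% loss it is 0.991² = 98%. At 20% loss it is 0.584² = 34%.

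**The case against.** The strongest reply is that the plan does carry an allowance. Recruiting up to 100 for 80 completers is the language of attrition, and 40 is simply half of 80, given in brackets while explaining race balance. Read as 40 completers per stratum, the conflict disappears. The CO and pregnancy checks also follow Virtual Visit 1, so some of the 100 may be lost before they count as enrolled.

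Part of this stands. A reader might infer that the plan makes no allowance for loss at all; the 100-to-80 sentence does not support that. What remains is that the stratum rule says enrolled, not completers, and no replacement rule repairs it. Either the rule cancels the overage, or the overage covers only loss before enrolment.

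A second reply is that the consequence is small. That largely stands too. Power falls gradually: at n=79 Aim 2 power is still 79.3%. For Aim 1, d=0.31 is the smallest detectable effect, not the one anticipated. For Aim 2, a true difference of 0.1 SD takes power to about 64% with no loss at all, so the zero-difference assumption matters more than 10% loss.

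**Conclusion.** The inconsistency is real and should be corrected, but its effect is modest. As written, the cap delivers the 80 used in the power calculation only if nobody enrolled is lost before contributing the modelled marketplace data. At an assumed 5% to 10% loss, Aim 2 power falls from 80% to 77% or 74%, about 3 to 6 points. These are complete-case figures at a true difference of zero, and the mixed model would recover some of the shortfall.

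Two stronger conclusions are tempting and unsupported. One is that the trial should expect 67% power for Aim 2: that needs the whole 100-to-80 gap to be loss after enrolment and before the Conditions 1-3 data, and nothing in the document says so. The other is that Aim 1 is in danger: at the anticipated d=0.5 it keeps 97.6% power at n=64. I am confident of the inconsistency; the size depends on loss rates after enrolment that the plan does not give.

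**What to change.** Reconcile the two statements under Subject Selection Criteria in one of two ways.

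(a) Close each stratum at 40 participants who provide the marketplace data for Conditions 1-3 with menthol cigarettes unavailable, with a ceiling of 50 enrolled per stratum (2 × 50 = the existing 100). State that the 100 counts enrolled, eligible participants.

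(b) Keep the cap of 80 enrolled and restate the power for Aims 1 and 2 at the number expected to provide data.

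Either way, state the expected loss, and align the N=80 in Overall Study Design with the choice made.

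**Cost.** A few sentences. Option (a) means up to 20 more enrolled than the present cap, and the strata may end slightly unequal in numbers enrolled. It works well at 5% to 10% loss, but at 20% a ceiling of 50 fills both strata only about 34% of the time, so (b) would also be needed. Option (b) costs only a slightly lower stated power.
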